CONFIDENTIAL

VERITAS

THO 19102: NaVigation Endoscopy to Reach Indeterminate lung nodules versus Transthoracic needle Aspiration, a randomized controlled Study (VERITAS)

Principal Investigator:

[name]

Professor of Medicine and Thoracic Surgery
Associate Professor of Mechanical Engineering
Vanderbilt University School of Medicine

Co-Principal Investigator:

[name] DPhil MSc FRCP
Professor of Respiratory Medicine
Oxford Centre for Respiratory Medicine
Clinical Director, Oxford Respiratory Trials Unit
University of Oxford

Protocol Version 29MAR2023

CONFIDENTIAL

PROTOCOL SYNOPSIS

Title	Navigation Endoscopy to Reach Indeterminate lung nodules versus Transthoracic needle Aspiration, a randomized controlled Study
Short title	VERITAS
Study objective	In this study, we propose to study in a 1:1 randomized controlled trial the diagnostic accuracy of navigation bronchoscopy pathway with fluoroscopic navigation (F-Nav) using a non-inferiority study design (primary endpoint) versus the current clinical standard of care: CT-guided biopsy.
Study device	SuperDimension and Fluoroscopic navigation.
Design	Multicenter, randomized, non-inferiority study.
Study centers	Vanderbilt University Medical Center, and approximately 5 to 7 additional sites based in the United States.
Number of subjects	N=258
Subject follow-up	Patients with non-diagnostic biopsy or benign diagnoses will be followed for up to one year as part of the study with further diagnostic procedures as clinically required.
Inclusion criteria	
1. ≥ 18 years of age at time of signing informed consent.2. Referred for biopsy of a single indeterminate pulmonary nodule, with the following characteristics regarding size, location, accessibility, and probability of malignancy:
a) Intermediate or high pre-test probability of malignancy as defined by a pre-test probability of malignancy between 10% and 100%, using a validated clinical prediction model, which is either:
i. The Brock model if no PET scan data are available, orii. The Herder model if PET-CT data are available.b) Size between 10 and 30 mm (long diameter).c) Location peripheral, here defined as occupying the middle or outer third lung zones.d) Accessible via navigation bronchoscopy and also accessible via CT-guided biopsy (i.e. the nodule is clinically suited to equal access by either procedure), as confirmed by an independent interventional panel (see Section 4.5).
Exclusion criteria	
1. Patients with proximal nodules, as defined by nodules accessible via conventional bronchoscopy (endobronchial lesions) or linear endobronchial ultrasound will not be eligible for the study (as these patients would standardly undergo bronchoscopy already).2. Patients with multiple nodules requiring biopsy (patients may have other nodules not considered for biopsy).3. Radiologically abnormal mediastinal or hilar lymph nodes requiring endobronchial ultrasound.4. Patients for whom stereotactic body radiation therapy is planned even if biopsies show no evidence of malignancy.5. Patients with contraindication to biopsy or deep sedation/general anesthesia.6. Patients unable or unwilling to comply with study follow-up schedule.7. Patients previously randomized to the study.8. Patients unable to provide documented informed consent.9. Patients who are pregnant or nursing.

CONFIDENTIAL

Primary endpoint	
The primary endpoint will be diagnostic accuracy, as defined by the rate of technically successful biopsies leading to a definitive diagnosis, comparing the bronchoscopy pathway (navigation bronchoscopy) to the CT-guided biopsy pathway. Definitive diagnoses are pre-defined as any of the following:
 
• Malignancy on histology, OR• Biopsies with abnormal tissue (excluding normal or absence of lung parenchyma) that are followed by a surgical lung biopsy yielding the same histological diagnosis, OR• Specific benign histopathologic finding which accounts for the presence of a lung nodule (specifically including organizing pneumonia, frank purulence, granulomatous inflammation, or other specific benign finding) AND• Absence of malignancy (true negative) through 1-year longitudinal CT follow-up, defined as:
◦ The nodule markedly regresses or resolves on follow-up imaging, OR◦ a persistent nodule has not been diagnosed as malignant, AND◦ there are no plans for repeat invasive diagnostic procedures through 12 months follow-up. 
Biopsies with normal or absence of lung parenchyma, atypia and non-specific inflammation will be considered non-diagnostic. All biopsies not diagnostic of malignancy (from both arms) will be centrally reviewed by an independent expert lung pathologist blinded to the biopsy technique, and follow-up diagnosis will be established during routine clinical follow-up after 1 year.

Secondary endpoints	
• Rate of pneumothorax.• Rate of pneumothorax requiring chest tube placement.• Clinically significant bleeding (defined by bleeding requiring intervention).• Need for hospitalization after procedure.• Duration of the procedure.• Procedural factors associated with improved yield (type of biopsy, number of biopsies, use of radial ultrasound, presence of a bronchus sign, biopsy site).• Need for additional nodule biopsy.• Need for additional procedure for staging.• Radiation exposure from fluoroscopy-guided bronchoscopy and CT for CT-guided biopsy.• Need for F-Nav during navigation bronchoscopy.• Diagnostic yield, defined as the rate at which histopathology is obtained which explains the presence of a nodule (according to definitions set forth for the primary endpoint) and permits post-biopsy clinical decision-making without need for immediate additional diagnostic procedures.• Rate at which the biopsy procedure yields a confident clinical diagnosis (including any added yield from endobronchial ultrasound-guided mediastinal and/or hilar lymph node biopsies or microbiologic studies which yield an explanation for a nodule despite non-diagnostic biopsy specimens).

CONFIDENTIAL

Statistical methodology	The primary analysis will use a Bayesian approach, the initial power analysis uses a Frequentist approach. We assume that diagnostic accuracy for CT-guided biopsy is 90%. The non-inferiority margin is set at 10 percentage points, and one-sided type I error rate is set at 5%. Thus, if the true diagnostic accuracy for navigation bronchoscopy is lower than 80%, we will have 5% probability (type I error rate) to incorrectly conclude noninferiority.
Interim analysis	No interim analyses are planned for this trial.

CONFIDENTIAL

Table of Contents

1. General Study Information	8
2. Statement of compliance.....	8
3. Purpose of the study	8
3.1 Hypothesis.....	8
3.2 Aims and Objectives	9
4. Study Design	10
4.1 General Study Design.....	10
4.2 Patient Inclusion and Exclusion Criteria.....	10
4.3 Withdrawal of Patients	11
4.4 Patient Flow	12
4.5 Image Transfer and Interventional Panel Adjudication.....	12
4.6 Intervention Arm: Bronchoscopy Pathway	14
4.7 Comparison: CT-guided Biopsy Pathway	14
4.8 Outcomes	15
4.9 Centralized Pathology Review (Core Lab Confirmation).....	16
4.10 Study Flow	16
5. Enrollment Procedures.....	16
6. Methodology	18
6.1 Statistical methodology	18
6.2 Analysis plan.....	19

3.1 Hypothesis

Lung cancer accounts for more cancer-related deaths in the US than colon, prostate and breast cancer combined, representing approximately 160,000 deaths every year.¹ In 2011, the National Lung Screening Trial (NLST) demonstrated a 20% relative reduction in lung cancer mortality with annual low-dose computed tomography (LDCT).² These encouraging results, which were recently confirmed in a large European randomized controlled trial on lung cancer screening, the NELSON trial, have led to the widespread endorsement of lung cancer screening, but implementation is hampered by the high rate of false-positive LDCT studies.³ An estimated 1.5 million new indeterminate lung nodules are identified every year on chest computed tomography (CT) in the US, translating to around 4,000 nodules per day in the US alone, and implementation of LDCT-based lung cancer screening is estimated to increase these numbers substantially, as more than 10 million US adults are candidates for screening based on accepted eligibility criteria.⁴ In the NLST, approximately 40% of individuals randomized to LDCT screening had one or more nodules identified during the study period, the vast majority of

CONFIDENTIAL

which were ultimately proven benign.² This means that the diagnosis and management of pulmonary nodules will be an enormous and increasing healthcare need of the future.

The diagnostic algorithm for indeterminate pulmonary nodules is based on pre-test probability of malignancy as determined by validated clinical prediction scores or clinician estimates. Low-probability (<10% chance of malignancy) are followed radiologically with serial CT, while high pre-test probability nodules (>70% chance of malignancy) are typically surgically resected, although tissue confirmation is often necessary even for these nodules.⁵ A non-surgical biopsy is typically recommended for nodules with low to intermediate probability of malignancy. High pre-test probability nodules are also frequently biopsied, when surgery is considered higher-risk or when stereotactic body radiation therapy is considered. Options include CT-guided transthoracic needle biopsy or bronchoscopic biopsy. CT-guided biopsy is associated with a general yield estimated at 90%, although studies focusing on nodules < 1.5 cm have reported yields between 70% and 80%.⁶⁻⁸ There has not been randomized controlled studies comparing CT-guided biopsy to other approaches. The technique is associated with substantial complications: in a population-based study, the rate of pneumothorax was 15% with need for chest tube management in 7%, and the risk of hemorrhage was 1%.⁹ Conversely, bronchoscopic biopsy is safer with reported 1.6% pneumothorax, with a need for chest tube management in 0.7%, and a 0.5% hemorrhage risks, but best estimates of yield using conventional navigation techniques approach 75%, with rates below 50% in registry data.¹⁰⁻¹²

One of the main limitations of navigation bronchoscopy is the inability to confirm successful navigation, as the roadmap planning to the nodule is based on preoperative CT images obtained at lung volumes substantially different than those achieved during deep sedation or general anesthesia required during bronchoscopy. The recently introduced FDA-approved enhanced fluoroscopy imaging device, F-Nav (SuperDimension, Medtronic, Minneapolis, Minnesota, USA), allows visualization of fluoroscopically-invisible nodules, re-registration and adjustment of the target. Using this more “real time” technique, the diagnostic yield approaches 85% in retrospective data from Vanderbilt University Medical center, Nashville, TN. In addition, endobronchial ultrasound biopsies of mediastinal lymph nodes are diagnostic in 13% of patient without CT or PET scan abnormalities, which emphasizes the importance of bronchoscopy.¹³ If these promising results were confirmed, the widespread adoption of F-Nav would allow diagnostic resolution of indeterminate pulmonary nodules with the following advantages over CT-guided biopsy: (1) avoidance of potentially life-threatening complications associated with CT-guided biopsies, (2) performance of complete mediastinal staging via endobronchial ultrasound when malignancy is confirmed, in a single procedure under a single sedation / anesthetic session and (3) potential biopsy of multiple indeterminate lung nodules in the same procedure. This has the potential to significantly decrease mortality, morbidity and healthcare costs, and if proven, to be a robust diagnostic methodology, to become the standard of care for thousands of patients per year.

3.2 Aims and Objectives

In this study, we propose to study in a 1:1 randomized controlled trial the diagnostic accuracy of navigation bronchoscopy (NB) with F-Nav (SuperDimension iLogic 7.2 ENB platform and later (SuperDimension, Medtronic, Minneapolis, Minnesota, USA)) using a non-inferiority study design (primary endpoint) versus the current clinical standard of care: CT-guided biopsy. We will in addition compare: complications rate including rate of pneumothorax and clinically significant bleeding, need for hospitalization

CONFIDENTIAL

after procedure, time to procedure, duration of the procedure, need for additional nodule biopsy, need for additional procedure for staging, radiation exposure from fluoroscopy and CT, and need for F-Nav during navigation bronchoscopy (secondary endpoints). Follow up has been chosen to be pragmatically deliverable while allowing full assessment of key outcomes, including false negatives to provide a robust, clinically meaningful trial result.

4. Study Design

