The LungCloud™ allows each site's clinical study coordinator to manage patients that have to be added to the clinical study. Informed consent can be electronically acquired or added manually in the system. After informed consent has been obtained, the patient's de-identified data will be shared with the study primary site.

As part of the study, the subject's chest CT will be displayed in the clinical study review web-portal for analysis by the independent interventional panel consisting of (1) an interventional pulmonologist expert in navigation bronchoscopy and (2) an interventional radiologist expert in CT-guided biopsy. The lung nodule will be assessed for its location in the proximal, middle or outer third of the lung by an independent expert lung nodule physician using a validated software analysis. Nodules accessible by ultrasound guided TTNA, conventional bronchoscopy or linear EBUS will be excluded. Nodules located in the middle or distal third will be included. If

CONFIDENTIAL

the nodule is deemed amenable to both bronchoscopic and CT-guided biopsy approach, the patient will be randomized.

This assessment involving central review by the interventional panel is intended to occur within **3 business days** after informed consent is obtained. Subsequent randomization of eligible patients is anticipated in conjunction with confirmation of enrollment (as outlined below in Section 5), with initiation of navigation bronchoscopy or CT-guided biopsy to occur within 3 weeks (30 calendar days) after a site is notified of randomization. In the event that a CT scan cannot be uploaded to LungCloud™ expeditiously enough for adjudication to occur within the mandatory 3 day post-informed consent window, central adjudication will proceed using one or multiple representative axial CT slices uploaded to CRF 2 in the study REDCap database.

[figure not shown]
Exclusion criteria for accessibility via navigation bronchoscopy:

1. Nodules with an airway greater/equal to 3 cm away from the lung nodule
2. Nodules located in areas deemed unreachable by an expert interventional bronchoscopist

Exclusion criteria for accessibility via CT-guided biopsy:

1. All nodules for which a fissure would have to be crossed
2. All nodules for which a large bulla would have to be crossed
3. All nodules located in areas deemed unreachable by expert interventional radiologist

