Please contact the assigned Study Contact with any questions regarding this process. You can also reach out to your assigned CRA once the study is activated.

The VICC Coordinating Center will assign Subject ID numbers to all patients whose eligibility has been confirmed. Only patients deemed eligible will be registered to the study. Sequence/study ID numbers will not be re-used if a patient screen fails. Following registration, eligible participants should begin the study consistent with the protocol no later than 28 days after registration/enrollment by the VICC Coordinating Center.

Following registration, eligible participants should initiate navigation bronchoscopy or CT-guided biopsy no later than 30 business days after the site is notified of randomization by the VICC Coordinating Center. If a participant does not receive the procedure following randomization within the allowed time period, the patient may be re-consented or participant's registration on the study will be canceled. The Study Contact should be notified of cancellations as soon as possible.

The purpose of this 30 business day scheduling window is to protect subjects from being randomized to a procedure which overly delays their care, when the alternative procedure could be performed substantially sooner and would otherwise have been utilized in clinical practice outside of this trial. For example, if biopsy procedure #1 cannot be performed for 8 weeks due to local factors (equipment failure, perhaps), but biopsy procedure #2 could be performed within two weeks, the 30-day window protects this patient from a potentially harmful delay in a malignant diagnosis by removing them from the trial so they may proceed with procedure #2 on clinical grounds. However, if a situation arises in which a patient must be scheduled outside the 30-day window but 1) the alternative procedure cannot be performed meaningfully sooner and 2) the delay in biopsy is

CONFIDENTIAL

not expected to impact any eligibility criteria, the patient may remain in the trial (an example in which point #2 might be invoked: a patient with a 29 mm nodule delayed for 3 months, a sufficiently long interval of time in which the nodule may well have grown to exceed 30 mm diameter and therefore no longer be eligible for the trial). This determination must be agreed upon by both the local PI and the central PI ([name]) and will be documented in the "notes" field at the end of REDCap CRF #1.

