6.3 Variables Recorded

- Past medical history
- Demographic data
- Smoking history
- Occupational history
- Current medications
- Laboratory data (complete blood count, electrolytes, creatinine, coagulation profile if available, results of fungal serologies if available)
- Chest CT characteristics:
 - Location of the nodule (lobe and segment)
 - Nodule size (longest axis)
 - Distance to the nearest visible bronchus on either CT plane (axial, coronal or sagittal)
 - Bronchus sign (airway aligned with nodule)
 - Distance to the nearest parietal pleura
- PET scan characteristics (FDG uptake (SUV))
- Procedural characteristics:
 - Duration of procedure
 - Number and type of biopsies
 - Use of FluoroNav, and divergence in mm if used
 - Radiation exposure
 - Complications (pneumothorax, bleeding, others)
- Time to procedure (delay between decision to biopsy and procedure)
- Time from identification of nodule to treatment for malignant nodules
- Need for another biopsy modality
- Need for an additional staging procedure
- Follow-up data.

7. Safety Reporting of Adverse Events

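### Time to procedure is compared between arms in Section 3.2, but Section 5 can remove late patients after randomization, which biases any difference toward zero by an amount the documents do not fix

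*Combined protocol and SAP*

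**What the plan says.** **Endpoint status.** Section 3.2 says the arms will be compared on a list that includes "after procedure, time to procedure, duration of the procedure, need for additional nodule biopsy" and labels the list as secondary endpoints. The endpoint lists in the synopsis and Section 4.8 leave time to procedure out.

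**Definition.** Section 6.3 lists it among the recorded variables: "Time to procedure (delay between decision to biopsy and procedure". The interval ends with the procedure, and no value is defined for a patient who does not have it.

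**Removal.** Under Section 5, if the procedure is not done in the allowed time, "the patient may be re-consented or participant's registration on the study will be canceled". The stated purpose is to protect a patient whose assigned procedure is slow when the other could be done substantially sooner, "by removing them from the trial so they may proceed with procedure #2 on clinical grounds". A late patient may stay if the alternative is not meaningfully sooner and the delay is not expected to affect eligibility, with agreement of the local and central principal investigators.

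**Window.** It is stated in several ways: "within 3 weeks (30 calendar days) after a site is notified of randomization" in Section 4.5; "no later than 30 business days after the site is notified of randomization" in Section 5; and, also in Section 5, a requirement to "begin the study consistent with the protocol no later than 28 days after registration/enrollment". Section 5 later speaks of a 30-day window without saying which kind of day.

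**Analysis.** Section 6.2 makes the per-protocol population the analysis set. In the intention-to-treat sensitivity analysis it scores dropouts without final data as treatment failures, which does not supply a waiting time. No method, censoring rule or handling of removed patients is given for time to procedure.

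**The concern.** Removal happens after randomization and depends on two things: how long the wait for the assigned procedure is, and whether the other arm's procedure is faster. The first is the endpoint (its post-randomization part) and the second is the contrast the endpoint is meant to measure. A comparison restricted to patients who had the procedure therefore drops long waits selectively, and drops more of them from whichever arm is slower.

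The exception does not repair this. It keeps late patients for whom both routes are slow, whose waits say little about the difference between arms. It lets go those for whom one route is slow and the other is not, whose waits say the most.

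At stake is a secondary result on access. Section 5 itself treats an avoidable delay as potentially harmful, and the planned comparison would understate it. The primary endpoint is not the subject of this point.

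**Working it through.** **The plan's own figures.** The documents give no figure for time to procedure. The primary sample size reproduces: (1.645 + 0.842)² × 2 × 0.9 × 0.1 / 0.1² ≈ 111.3, so 112 per group. It has no bearing here.

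**Inputs.**
- Window: 30 calendar days (Section 4.5), or 30 business days (Section 5), which is six working weeks, about 42 calendar days.
- Waits after randomization: not given. Assumed log-normal with log-SD s = 0.6, median 14 days in the faster arm and 21 in the slower. Which arm is slower is left open.

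**Formulas.** With m the median, W the limit and a = (ln W − ln m)/s:
- share removed = 1 − Φ(a)
- mean of observed waits = m·exp(s²/2)·Φ(a − s)/Φ(a)
- median of observed waits = m·exp(s·Φ⁻¹(Φ(a)/2))

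**No truncation.** The means are 14 × 1.197 = 16.8 and 21 × 1.197 = 25.1 days. The mean difference is 8.4 and the median difference 7.0.

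**All waits beyond W removed.**

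| Limit | Arm median | a | Removed | Observed mean | Observed median |
|---|---|---|---|---|---|
| 42 | 14 | 1.831 | 3% | 15.4 | 13.7 |
| 42 | 21 | 1.155 | 12% | 20.4 | 19.1 |
| 30 | 14 | 1.270 | 10% | 14.0 | 13.0 |
| 30 | 21 | 0.594 | 28% | 17.3 | 17.0 |

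- 42-day limit: mean difference 4.9 of 8.4 days (59%); median difference 5.5 of 7.0 (78%).
- 30-day limit: mean difference 3.3 of 8.4 days (39%); median difference 4.0 of 7.0 (58%).

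With a slower-arm median of 28 days, the true mean difference of 16.8 becomes 8.2 (42 days) or 5.3 (30 days).

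**With the Section 5 exception.** Suppose a late patient is removed only if the alternative is at least 7 days sooner (the 7 days is an assumption). By simulation for medians 14 and 21:
- A patient's two waits independent: mean difference 4.9 (42 days) and 3.3 (30 days), unchanged. The median differences are 5.5 and 4.1.
- Correlation 0.8 between a patient's two waits: mean difference 4.4 and 2.3, smaller still, because the exception then keeps more long waits in the faster arm.

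**Wider range.** Slower-arm medians of 17.5, 21, 28 and 42 days against 14, with log-SD 0.5 and 0.8, were also simulated. A 42-day limit keeps 42% to 91% of the true median difference; limits of 28 to 30 days keep 25% to 74%. The difference shrank in every scenario.

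**The case against.** The strongest reply is that the documents do not show how large this is. They give no waiting times and do not say either arm is slower; the Section 5 example is hypothetical and leaves its two procedures unnamed. That stands, and it rules out some stronger readings:

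- A reader might infer that the slower arm will look nearly as fast as the other, or that the trial will report similar access times. The documents do not support this. With the longer window and the base assumptions, 78% of the median difference survives. That is attenuation, not disappearance.
- A reader might infer that all the longest waits are lost. Section 5 also offers re-consent, and its exception keeps some late patients. It does not say how a re-consented patient's wait would be counted.
- A reader might take the truncation figures as a worst case because the exception retains patients. The simulation shows otherwise: modelling the exception leaves the difference unchanged or smaller.
- A reader might think that starting the clock at the decision to biopsy is itself the bias. It is not. The part before randomization is balanced in expectation and adds noise; it also means that the window limits only part of the recorded interval.

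The larger scenarios also fit the plan poorly. At a 30-day limit the base case removes (28% + 10%)/2 = 19% overall for delay alone, against 15% planned attrition from all causes. At 42 days it removes (12% + 3%)/2, about 8%.

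Finally, the endpoint is missing from both formal lists, so it could be called descriptive only. But Section 3.2 says plainly that it will be compared, and that has not been withdrawn.

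**Conclusion.** The point holds in a limited form. As written, the plan compares time to procedure between arms, defines it only for patients who had the procedure, and allows removal after randomization for reasons tied to both the wait and the arm. The direction of the bias, toward no difference, follows from those rules and appeared in every scenario run. The size does not follow from the documents. The base-case loss of 3.5 days (8.4 to 4.9) or 5.1 days (8.4 to 3.3) in the mean rests on assumed log-normal waits and on which window applies. This is a secondary endpoint of unsettled status, and nothing here bears on the non-inferiority conclusion. It is still worth correcting before analysis, because following the current text yields a biased comparison and the remedy is cheap.

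**What to change.** 1. Reconcile Section 3.2 with Section 4.8 and the synopsis: either list time to procedure as a secondary endpoint in all three, or remove it from the comparison in 3.2.
2. If it is kept, analyse all randomized patients by assigned arm, as the cumulative proportion who have had the assigned procedure over time since randomization. Count patients cancelled, removed or switched to the other procedure as a competing outcome, not as missing. Simple censoring at cancellation would be weaker, since it assumes that these patients would have waited no longer than those who stayed. State how re-consented patients are counted.
3. Report by arm the number removed for delay and the number kept under the Section 5 exception.
4. Keep the interval from decision to biopsy as a descriptive measure.
5. Reconcile the window statements in Sections 4.5 and 5. No change to the scheduling rule is proposed, and this point does not say which window is right.

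The cost is wording in Sections 3.2, 4.8 and 6.2 and the synopsis. The one practical condition is that the database holds dates of randomization, procedure and cancellation. Section 4.7 provides for recording the cause of a cancelled procedure, but the documents do not confirm that the cancellation date is captured; if it is not, a field is needed.
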